7.3. Definition of RLS Refractory to Medication (IC #2)

For inclusion criterion #2, the following definition of refractory will be used:

The patient has failed at least one prescription medication administered to treat RLS* for one or more of the following reasons, as determined by the investigator:

- 1. Adverse effects associated with the medication are intolerable.
- 2. Patient exhibits symptoms of augmentation.

3. Efficacy has reduced to the point where an up titration would be needed to maintain a sufficient response to medication.

4. The patient lacks sufficient response to medication at the maximum approved or recommended dosage.**

5. The patient lacks sufficient response to medication at the maximum tolerable dosage due to adverse effects.

*Failure of any of the following prescription medications is sufficient to demonstrate that a patient is refractory: Ropinirole (FDA-approved), Pramipexole (FDA-approved), Rotigotine (FDA-approved), Gabapentin enacarbil (FDA-approved), Pregabalin (not FDA-approved for RLS, but administered in clinical practice), Gabapentin (not FDA-approved for RLS, but administered in clinical practice). ** per FDA-approved dosage regimen or per RLS consensus statement in the case of off-label medications (Pregabalin or Gabapentin).

8. Investigational Device

8.1. Description

The NTX100 Neuromodulation System is positioned and worn bilaterally on the legs with stimulation electrodes over the head of the fibula bone, thus targeting the common peroneal nerve – this nerve target innervates regions of the lower extremities commonly associated with RLS symptoms. For each leg, the NTX100 Neuromodulation System consists of (1) one stimulation unit, (2) two or more electrode areas, and (3) a mechanism for attachment to leg, described below.

- The (1) stimulation unit will:
 - o be battery-powered and contain a rechargeable battery and connector for recharging,
 - o contain a circuit board that generates the stimulation waveform,
 - o contain controls that the subject can use to activate stimulation,
 - contain controls that the subject can use to adjust the intensity of stimulation within a range programmed by the researcher,
 - contain an electronic connection mechanism to deliver a stimulation waveform to the electrodes,
 - contain an interface that the researcher can use to program the range of stimulation intensities, program the mode of stimulation (active or sham), and download data on compliance and functionality.
- The (2) electrodes areas will each:

CONFIDENTIAL

- o be an electrolyte-containing medium or a hydrogel material,
- be disposable, allowing for at least 1 night of use by one subject,
- be attached to the stimulation device by using snaps, magnetic connectors, conductive adhesives, shielded or insulated wires, hook and loop fasteners, or similarly secure connectors,
- \circ have an electrode surface area between 5cm2 and 50cm2.
- The (3) attachment mechanism will:
 - secure the device containing the disposable electrode areas to the body via straps and/or additional biocompatible adhesives.

Description of stimulation parameter ranges allowed by protocol:

- Pulse amplitude: up to 45mA
- Frequency: 2kHz 6kHz
- Pulse width: 80 250 microseconds (depending on frequency)
- Duty cycle: 25-100%
- Pulse shape: Charge-balanced
- Duration: up to 60 minutes per session (up to 120 minutes per day)

8.2. Instructions for Use and Administration

Use of the NTX100 Investigational device is described briefly herein. For details see Instructions for Use.

8.2.1. Route of administration

The NTX100 Neuromodulation System is designed to stimulate the common peroneal nerve; stimulation electrodes within the device are positioned superficially and bilaterally on the lower legs over the head of the fibula bone, a position where the peroneal nerve is close to the skin. This nerve target innervates regions of the lower extremities commonly associated with RLS symptoms.

8.2.2. Dosage and dosage regimen

CONFIDENTIAL

The dosage regimen depends on the intensity, timing, and duration of stimulation:

1. Intensity. The setpoint stimulation intensity may be the lesser of (a) the maximal intensity that the subject reports is non-distracting and comfortable, as determined in the calibration session described in the instructions for device use and (b) the maximal intensity for each set of stimulation parameters, as determined based on device output capabilities. Subjects may be allowed to adjust stimulation intensity from the setpoint stimulation intensity, but only within a limited pre-programmed range. For example, the subject may increase intensity if symptoms are severe or reduce intensity if symptoms are mild.

2. Timing. Subjects may be instructed to administer stimulation primarily after RLS symptoms become noticeable and before the RLS symptoms become severe.

3. Duration. Each session of stimulation may last 30 minutes. Stimulation may be activated for up to 120 minutes per day (e.g., up to 4 x 30-minute sessions), depending on the timing, duration, and severity of RLS symptoms for the specific subject.

8.3. Contraindications

The following are contraindications to device usage:

- Diagnosis of epilepsy or other seizure disorder,
- Active medical device implant anywhere in the body, including but not limited to pacemakers, spinal cord stimulators, deep brain stimulators
- Metal implant at the site of study device application
- Known allergy to device materials (or severe previous reaction to medical adhesives or bandages)
- Cellulitis, open sores, or acute injury at or near the location of device electrode application

9. Risks

9.1. Investigational device risks

NPNS devices such as NTX100 Neuromodulation System result in a known potential for the following anticipated observations, which are typically mild to moderate, transient in nature, and resolve over time.

- Mild skin irritation from use of adhesive electrodes and/or secondary attachment mechanism.
- Discomfort, paresthesia, or otherwise irritating or uncomfortable sensations during active electrical stimulation.
 - This risk is reduced by calibrating the stimulation intensity.
- Temporary interference with sleep while wearing the device:
 - For some individuals, device may be uncomfortable, thus interfering with sleep while wearing the device.
 - For some individuals, this device may interfere with preferred sleep positions, thus interfering with sleep during usage.
- Temporary increase in RLS symptoms while wearing the device:
 - For some individuals, this device may interfere with voluntary leg movements used to relieve RLS symptoms, thus leading to a temporary increase in RLS symptoms.
 - In some cases, this device may otherwise lead to a temporary increase in RLS symptoms during active stimulation for other reasons.
 - This risk may be reduced by calibrating the stimulation intensity and/or adjusting the schedule of stimulation.

10. Adverse Events

Anticipated observations (e.g. common treatment effects) and adverse events occurring during the study will be recorded. Descriptions of anticipated observations and AEs will include the date of onset, the date it ended, the severity, the relationship to study device, and the outcome. All reported AEs will be summarized by the number of subjects reporting AEs, system organ class (where applicable), severity, seriousness, and relationship to study device.

The study Investigator and Coordinator will evaluate, characterize and record in the electronic Case Report Form (eCRF) all adverse events (AEs) occurring in all subjects from the time of enrollment to study exit (or premature withdrawal). Adverse events unresolved at study exit will be followed by the Investigator until resolution occurs or at least 60 days after the subject's participation in the study is complete. AEs may be reported spontaneously by the subject or detected by the Investigator or Coordinator. AEs should be evaluated for diagnoses not just symptoms (i.e., "angina", not "chest pain").

In addition to verbatim terms, the Sponsor may categorize all AEs using MedDRA preferred terms (PT) and system organ classes (SOC). Analysis may report both verbatim and MedDRA terms.

10.1. Adverse Event Definitions

An **adverse event** (AE) is any untoward medical occurrence, independent of its association with the investigational device. AEs also include any adverse laboratory signs or physical exam findings.

A serious adverse event (SAE¹) is any AE that:

- led to a death,
- led to a serious deterioration in the health of the subject that:
 - resulted in a life-threatening illness or injury,
 - resulted in a permanent impairment of a body structure or a body function,
 - required in-patient hospitalization or prolongation of existing hospitalization,
 - resulted in medical or surgical intervention to prevent permanent impairment to body structure or a body function
- or led to fetal distress, fetal death or a congenital abnormality or birth defect.

A **device-related SAE** is an event meeting the SAE definition above that is also rated as probably or definitely related the investigational device. No device-related SAEs have been reported in prior studies. Note that an elective or pre-planned hospitalization for a condition that did not worsen during the study is not an AE.

An **unanticipated serious adverse device effect** (USADE) is any SAE that is caused by, or associated with, a device, if that effect, problem, or death was not previously identified in nature, severity, or degree of incidence in the investigational plan or application (including a supplementary plan or application).

¹ Definition from ISO14155:2011

10.2. AE Severity and Relatedness

Each AE occurring in the study will be characterized by the study Investigator as to severity (Table 1) and relatedness (Table 2).

Table 1. AE Severity Grading System.

Grade	Brief description
Grade 1	Mild; asymptomatic or mild symptoms; clinical or diagnostic observations only; intervention not indicated
Grade 2	Moderate; minimal, local, or non-invasive intervention indicated; limiting age- appropriate instrumental ADL ^a
Grade 3	Severe or medically significant but not immediately life-threatening; hospitalization or prolongation of hospitalization indicated; disabling; limiting self-care ADL ^b
Grade 4	Life-threatening consequences; urgent intervention indicated
Grade 5	Death related to adverse event

^a'Instrumental ADL' refers to activities of daily living such as preparing meals, shopping for groceries or clothes, using the telephone, and managing money. ^b'Self-care ADL' refers to bathing, dressing and undressing, feeding oneself, using the toilet, taking medications, and not being bedridden. From the National Cancer Institute Common Terminology Criteria for Adverse Events v4.0 NCI, NIH, DHHS. May 29, 2009 NIH publication #- 09-7473.

Table 2. AE Relatedness Grading System.*

Grade	Relationship of AE to study device	Description
5	Definite	An event that follows a reasonable temporal sequence from administration of the study device; that follows a known or expected response pattern to the study device; and that is confirmed by improvement on stopping.

All information contained in this document is confidential and is the sole property of Noctrix Health, Inc. Any reproduction in part or whole without the written permission of Noctrix Health, Inc. is prohibited.

		Clinical Trial	Document #: CT-3 (previously CT-04) Rev: 2.0 (Superseded Rev A) CC#: 660			
H E A L T	IX H Investiga	ational Plan, Protocol CT-3 (Pivotal Trial)				

4	Probable	An event that follows a reasonable temporal sequence from administration of the study device; that follows a known or expected response pattern to the study device; and that is unlikely to have been caused by concurrent/underlying illness or other drugs, procedures, or other causes.
3	Possible	An event that follows a reasonable temporal sequence from administration of the study device; that follows a known or expected response pattern to the study device; but may have been caused by concurrent/underlying illness, drugs, procedure, or other causes.
2	Unlikely	An event that does not follow a reasonable temporal sequence from administration of the study device; that does not follow a known or expected response pattern to the study device, or most likely was caused by concurrent/underlying illness, drugs, procedure, or other causes, because of their known effects.
1	Not related	An event almost certainly caused by concurrent/underlying illness, drugs, procedure, or other causes.

* AEs occurring before treatment with the study device will be categorized as unrelated to the study device.

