- 12. Subject has moderate or severe cognitive disorder or mental illness.
- 13. Subject has current diagnosis of iron-deficient anemia or history of iron-deficient anemia within the past year.
- 14. Subject has known allergy to device materials, electrode gel, polyurethane foam, or lycra (or severe previous reaction to medical adhesives or bandages).
- 15. Subject has severe edema affecting lower legs.
- 16. Subject has any of the following at or near the location of device application.
 - Acute injury
 - Cellulitis
 - **Open sores**

CONFIDENTIAL

All information contained in this document is confidential and is the sole property of Noctrix Health, Inc. Any reproduction in part or whole without the written permission of Noctrix Health, Inc. is prohibited.

- Other skin condition
- 17. Subject is on dialysis or anticipated to start dialysis while participating in the study.
- 18. During the NTX100 calibration process, which is identical for subjects in the active and sham arms, subject reports not feeling stimulation sensations up to an intensity of 30mA, the subject finds stimulation intensities less than 15 mA to be uncomfortable or distracting, or the device does not properly fit the subject.
- 19. Subject has received another investigational device or drug within 30 days before study entry, is planning to receive another investigational device or drug during the study, or is planning to change RLS medications during the study.
- 20. Subject has undergone a major surgery (excluding dental work) in the 30 days prior to study entry.
- 21. Subject is unable or unwilling to comply with study requirements.
- 22. Subject is pregnant or trying to become pregnant.
- 23. Subject has a medical condition not listed above that may affect validity of the study as determined by the investigator.
- 24. Subject has a medical condition not listed above that may put the subject at risk as determined by the investigator.

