16.4. Screening

Potential subjects will be screened for eligibility based on the criteria in Section 7 above. Device calibration (Section 16.5 below) will be part of the screening process, consistent with Exclusion Criterion #18. A potential subject who signs the study consent and is eligible will be assigned a study ID number, will be considered enrolled, and will count towards the study's sample size. Potential subjects who fail Exclusion Criterion #18 and experience an adverse event (AE) during device calibration will be assigned a study ID for the purpose of tracking this AE but will not be randomized to a treatment arm and will not count towards the study's sample size.

16.5. **Device calibration**

During screening, the stimulation intensity of the investigational device will be calibrated separated for each leg (left and right), using the demo calibration kit provided by the sponsor. If the subject does not fail Exclusion Criterion #18 during calibration the subject will be randomized within the EDC system, the calibrated values will be programmed into the investigational device kit that corresponds

CONFIDENTIAL

to the randomization number generated. The calibration process is designed to identify the maximally effective settings that are comfortable for each subject. The sponsor may administer the calibration and/or assist in administering the calibration.

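### The rule that grades every pre-treatment AE as unrelated can misgrade reactions to calibration stimulation, and AE recording may start too late to capture them

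*Protocol*

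**What the plan says.** Protocol Section 10.2 leaves causality to investigator judgement by default: "Each AE occurring in the study will be characterized by the study Investigator as to severity (Table 1) and relatedness (Table 2". The footnote to Table 2 then makes an exception by timing: "AEs occurring before treatment with the study device will be categorized as unrelated to the study device". It does not mention calibration.

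Section 16.4 says that device calibration "will be part of the screening process, consistent with Exclusion Criterion #18". That criterion (Section 7.2) turns on how the current is felt: "subject reports not feeling stimulation sensations up to an intensity of 30mA, the subject finds stimulation intensities less than 15 mA to be uncomfortable". Distraction at those intensities and poor device fit are further grounds for exclusion. Current is therefore delivered, and by the same process in both arms. Section 16.5 specifies a demo kit and places randomization afterwards: "If the subject does not fail Exclusion Criterion #18 during calibration the subject will be randomized within the EDC system". Section 16.8 allows calibration to be adjusted at device training, which follows randomization.

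On collection, Section 10 has sites record AEs "occurring in all subjects from the time of enrollment to study exit (or premature withdrawal". Section 16.4 defines enrollment: "A potential subject who signs the study consent and is eligible will be assigned a study ID number, will be considered enrolled". It adds one special rule: "Potential subjects who fail Exclusion Criterion #18 and experience an adverse event (AE) during device calibration will be assigned a study ID". The stated aim is to keep track of the event. Table 3 marks Adverse Events at EVAL 2 to EVAL 11 and not at EVAL 1.

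**The concern.** Section 9.1 lists skin irritation, and discomfort or paresthesia during stimulation, as known device risks. Calibration searches for the limit of comfort, so it is a natural place for such reactions to appear. A rule that attributes them to other causes because of when they happen works against the stated purpose of AE evaluation in Section 10.3, which includes understanding the device's safety profile.

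Three things are at stake: whether calibration reactions are captured at all, what causality grade they carry, and whether a serious one can be called a device-related SAE. Section 17.3.1 makes relationship to the device one of the axes of the safety endpoint, so the grade is used.

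**Working it through.** No formula applies and the plan states no figure to reproduce. The check sets the order of procedures beside the AE rules.

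1. **Order of exposure** (Protocol Sections 16.4, 16.5, 16.7, 16.8 and 16.13). Consent; screening, with calibration stimulation from the demo kit; randomization if the subject does not fail Exclusion Criterion 18; programming of the assigned kit; training, with possible adjustment of calibration; home use. Stimulation is first delivered before randomization.

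2. **Meaning of treatment.** Section 4 uses the word for the allocated Active or Sham mode in Phase 1 and open-label Active in Phase 2. Section 16.1 describes eight weeks of treatment at home, and Section 16.10 describes nightly self-administration. All of this comes after calibration. No section says that calibration counts as treatment, and the footnote's phrase is not defined.

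3. **The footnote applied.** Suppose paresthesia starts with the calibration current and stops when the current stops. By the Table 2 descriptions (timing, known response pattern, improvement on stopping) it fits grade 5, Definite. On the reading in step 2 the footnote makes it unrelated, although grade 1 is reserved for events almost certainly due to something else.

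4. **The SAE label.** Section 10.1 requires a rating of probable or definite for a device-related SAE. The note to SAP Table 3.1 also counts possible and missing. A forced grade of unrelated falls outside both.

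5. **Collection, by type of subject.**
   - Fails Exclusion Criterion 18 with an AE: given an ID and tracked, so the event is recorded and then meets the footnote.
   - Passes and is randomized: enrolled only once eligible, which includes passing calibration. On that sequence the reaction came before the recording window opened.
   - Screen-fails for another reason: no rule.

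6. **What reaches the SAP tables.** SAP Section 8.3 starts every AE table at randomization, so most events with onset at calibration fall outside them whatever their grade. Some reactions from before home use can fall inside: reactions to an adjustment at training (after randomization); delayed reactions after remote calibration, when programmed devices are then mailed (Protocol Section 18); and same-day events that cannot be ordered, because the Listing 4 shell shows dates without times.

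7. **Size.** Exposed: about 132 randomized subjects plus an unstated number of calibration failures. No AE rate at calibration is given. For scale only, assumed rates of 2% and 5% would give 132 × 0.02 = 2.6 and 132 × 0.05 = 6.6 events. Neither rate has support in the documents, so this is not an estimate.

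**The case against.** The strongest reply is that the footnote is only the ordinary rule that events before exposure are unrelated. The Table 2 grades speak of administration of the study device, and Section 7.2 calls the procedure NTX100 calibration, so an investigator could treat calibration as exposure and grade normally. This stands as a possible reading. It means that misgrading is not certain, but also that sites could grade the same reaction differently. Calibration uses a separate demo kit by default, while Section 18 allows the study devices themselves to be used for it.

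A second reply is that the collection gap is over-read. Section 16.13 describes Evaluation 1 as the enrollment visit and includes calibration in it, Section 10 speaks of AEs during the study, and the special ID rule suggests that calibration AEs are meant to be tracked. Again this is a fair reading, but it conflicts with the definition of enrollment in Section 16.4 and with the empty EVAL 1 cell. The supportable statement is that such reactions may not be recorded. An unrecorded event also receives no grade, so the two problems do not fall on the same event.

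A reader might infer more than the documents support:

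- *That the comparison of AEs between arms is biased.* Calibration is identical in both arms and precedes randomization.
- *That the by-relationship safety endpoint is wrong as a whole.* Most calibration-onset events lie outside its window.
- *That unanticipated serious device effects would be missed.* That definition in Section 10.1 turns on cause or association, not on the Table 2 grade. All recognized SAEs are reportable under Section 10.3, and Section 13.7 has the sponsor review relatedness and investigate each SAE.
- *That calibration is the only stimulation felt by Sham subjects in Phase 1.* Section 5 gives sham mode a ramp-up of about 30 seconds with noticeable sensations, and calibration may be adjusted at training.
- *That any discomfort at calibration is an AE.* Some of it is simply how the comfort limit is found.

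**Conclusion.** The concern holds in a limited form. The footnote sets causality by timing, relies on an undefined term and, on the protocol's usual use of that term, overrides the Table 2 criteria for reactions to calibration stimulation. The recording rules leave it unclear whether such reactions are captured in subjects who pass calibration or who screen-fail for a reason other than Exclusion Criterion 18.

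The harm is confined to AE capture, causality grades and the device-related SAE label. The efficacy analyses and the randomized safety comparison are untouched. The number of events cannot be derived from the documents. The conclusion rests on two readings: that treatment means the assigned or in-home phase, and that enrollment follows eligibility as Section 16.4 states. If the sponsor intends otherwise, the defect is one of wording, and the same edits settle it.

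**What to change.** - **Table 2 footnote:** make only AEs with onset before first exposure to any NTX100 stimulation automatically unrelated, with calibration and the demo kit counted as exposure. Grade all later AEs by the Table 2 criteria.
- **Section 10:** record AEs from the first calibration stimulation for every consented subject, whatever the later eligibility outcome, and align Section 16.4 with this.
- **Table 3:** mark Adverse Events at EVAL 1, with the same change in the SAP's schedule of assessments.
- **SAP:** add a separate listing of AEs from calibration to randomization, and leave the tables that start at randomization as they are.

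Once recording starts at calibration, the reworded footnote will govern few recorded events, but it removes the conflict with Table 2. The cost is a few wording changes, one AE prompt at a visit that already takes place, and one more listing. A few more AEs may be recorded and graded device-related.
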